STUDY TITLE: Effect of Subtle Energy Transmission and Tao Calligraphy Mindfulness Practice on Telomere Length in Peripheral Blood Leucocytes

A Follow-up Pilot Study

PRINCIPAL CLINICAL INVESTIGATOR:

Name: XX, MD, FRCS Department: Sha Research Foundation, San Francisco, California

PRINCIPAL RESEARCH INVESTIGATOR:

Name: XX, PhD Department: Sha Research Foundation, San Francisco, California

VERSION DATE:

Version 3 of 10th April 2023

RELATED STUDIES:

None

Note: Names of research participants were removed as per instructions on Clinical Trials Gov Website.

1.0 Purpose and rationale of the study:

OBJECTIVES

The study is intended to measure the effects and determine the efficacy of Tao Calligraphy mindfulness practice together with subtle energy transmission on increasing length of telomeres in peripheral blood leucocytes. In our previous studies, the participants who regularly practiced reported a decrease in symptoms of their illness as perceived subjectively, an improvement in laboratory results or other tests and observed signs of progress reported by treating clinician and expressed an increase in well-being as measured by standardized scientific questionnaires.

HYPOTHESIS

The research null hypothesis is that individuals who receive subtle energy transmission for improving telomere length in peripheral blood leucocytes, and who will regularly practice mindfulness with Tao Calligraphy for 3 months, will have no significant change in telomere length in follow-up analyses and will show no improvement of well-being or clinical status as measured by standardized scientific questionnaire Rand SF 36(s) at 3 and 9 months.

Tools such as the Minitab version 14 and PSPP/SPSS will be used to analyze the data from laboratory assessment and Research Questionnaires at the start and at 3 months and at the end of 9 months of participation in the study. Statistical test such as Anova will be used to evaluate the null hypothesis. The p-value will represent how unlikely the observed data would be if the null hypothesis were actually true and we will use them to reach conclusions. We set the confidence level at 95% and if we receive p < 0.05, then H0 is rejected.

The correlation coefficient will be used to determine any correlation between various factors (e.g., effects of age, sex, length, and frequency of mindfulness practices and others on outcome) and regression analysis to determine the relation of independent and dependent variables.

BACKGROUND

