2.0 RATIONALE

The study aims to acquire both basic and applied knowledge to which the primary purpose is gain the measurable data of individuals to mindfulness practice with Tao Calligraphy together with subtle energy transmission, specifically focused on the lengthening of telomeres in peripheral blood Leukocytes. Thus, proposing another method of prolonging life expectancy that could be integrated into conventional medical treatment and care.

THEORETICAL FRAMEWORK

Tao Calligraphy art has been intensively studied at Sha Research Foundation in the US and Canada since 2013, producing significant results in improving overall well-being and an efficacious intervention for individuals with chronic conditions. [1]. [2]. [3]. [4]. This is a unique style of moving meditation, where mindfulness (heightened awareness) is achieved by the combination of movement and focus on Calligraphy art. In this practice, the subjects trace the lines of calligraphy with fingers and simultaneously say loudly or silently an affirmation (mantra), which enables them to achieve deep concentration during wakefulness.

No risks or negative side effects of the transmission of pure energy given to human participants or meditation with Tao Calligraphy have been observed in these pilot projects and formal studies.

 [1]. [name], [name], E. A. Yamashiro, and Jaime Chow, Meditation using Calligraphy and Chanting Mantra Improves Quality of Life – a Two years study, European Journal of Integrative Medicine, Volume 48, 2021, 101965, ISSN 1876-3820, https://doi.org/10.1016/j.eujim.2021.101965. [2]. K. Balonwu, Comparative psychometric studies and questionnaires on the effects of Tao Calligraphy Tracing Meditation in patients with Unipolar Depression after 25 hours and 50 hours., European Journal of Integrative Medicine, Volume 48, 2021, 101964, ISSN 1876-3820, https://doi.org/10.1016/j.eujim.2021.101964.

[3]. Tao Calligraphy and Mantra Chanting Improves EORTC QLQ-30 Quality of Life Scores for Women Diagnosed with Breast Cancer, Society for Integrative Oncology (SIO) 2021 Annual Conference, Sept. 24-26, Baltimore, MD, USA.

[4]. Tao Calligraphy Tracing Meditation with Mantra Chanting Improves Scores of McGill Pain Questionnaire (SF-MPQ) in 3 months, Society for Integrative Oncology (SIO) 2021 Annual Conference, Sept. 24-26, Baltimore, MD, USA.

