The proposed research is a pilot project, based on experiential data obtained from several previous pilot and formal studies by our research teams and researchers from other institutions. It focuses on the effects of transmission of pure energy (blessing) and meditation on improving the length of human telomere in peripheral blood leucocytes. We believe, the study will provide further data to offer an integrative intervention for individuals seeking additional treatment that is of minimal risk and to maximize benefits to address condition.

METHOD

This study will determine the effects of transmission of a subtle energy and mindfulness practice with Tao Calligraphy as measured through subjective and objective evaluations of changes in the subjects by Laboratory assessment of Peripheral blood Leucocytes Telomere length and subjective changes in RAND SF 36 Questionnaires.

Design of the Study

The study will be performed as a Pilot follow-up study, should the 0 Hypothesis be successfully rejected, this study will be followed by a formal Double Blind Randomized Crossover Study.

We plan subjects may enter the study as a group and will have measurements done within short time frame from each other at beginning and at the end of 3 and 9 months.

As this is a pilot study, there will be no randomization into treatment and control group and all subjects will receive a transmission and then will be practicing Tao Calligraphy mindfulness daily during the 9 months. Every subject who is accepted into the study, will have blood sample taken for analysis and will fill Rand SF 36 Questionnaire. Afterwards, will receive transmission of subtle energy by [name] (or his designee) and will be instructed on how to practice mindfulness with Tao Calligraphy.

Every subject who is accepted into the study, will receive prior to the inception of practice transmission of pure energy (blessing) and will be instructed on how to practice meditations with Tao Calligraphy.

The study is conducted on an outpatient basis and includes:

- a telephone discussion (clarification of inclusion/exclusion criteria)
- signing of the consent/information; instruction in the study design and practicing the Tao Calligraphy-tracing meditation; first data collection questionnaires (Time 0)
- regular weekly meditation practices on Zoom with participants in the treatment arm

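### The trigger for the follow-on randomised trial rests on one null joining telomere change and SF-36 improvement, so an uncontrolled SF-36 gain alone can satisfy it

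*Combined protocol and SAP*

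**What the plan says.** The trigger is in section 2.0, under Design of the Study: "should the 0 Hypothesis be successfully rejected, this study will be followed by a formal Double Blind Randomized Crossover Study". No other criterion for the follow-on trial is given.

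The null is in section 1.0, Hypothesis. Participants "will have no significant change in telomere length in follow-up analyses and will show no improvement of well-being or clinical status", the latter measured by the SF-36 at 3 and 9 months. The threshold is "if we receive p < 0.05, then H0 is rejected" and the method is "Statistical test such as Anova will be used to evaluate the null hypothesis". Section 4.0 leaves the choice of parametric or non-parametric tests open.

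The purpose is stated in one direction only. The objective is to "determine the efficacy of Tao Calligraphy mindfulness practice together with subtle energy transmission on increasing length of telomeres". The rationale is "specifically focused on the lengthening of telomeres in peripheral blood Leukocytes" and, a little later, concerns the effect of "meditation on improving the length of human telomere in peripheral blood leucocytes". Section 4.0 also speaks of lengthening.

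The Method section lists telomere length and SF-36 side by side and does not rank them. It adds that "there will be no randomization into treatment and control group". The supplied text names no primary endpoint, deciding follow-up, SF-36 score, multiplicity adjustment, or rule for the case where one outcome is significant and the other is not.

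**The concern.** A null of the form A and B is false as soon as A or B is false. On that plain reading, three things can fire the trigger besides true lengthening:

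- chance;
- a self-reported SF-36 gain with no telomere effect, which expectation or the passage of time could produce when there is no control group;
- a significant telomere shortening, because the telomere part of the null is worded as no change in either direction, while the SF-36 part is worded as no improvement.

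The opposite reading, that every part must be rejected, creates a different problem: true lengthening without an SF-36 gain would not meet the trigger. The text does not choose between the readings, so the same data can meet the rule or miss it according to a choice made after the results are known. At stake is a randomised trial launched on a signal other than the one this study was set up to find.

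**Working it through.** **The plan's own figure.** The plan gives a 5% threshold and 10 to 20 participants, with no effect size, SD or power to reproduce. The 5% equals the rule's false-go rate only if exactly one test is made.

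**Assumptions.** The documents give no SDs or correlations. I assumed normal data at baseline, 3 and 9 months; SD of change 1 at each follow-up; correlation between the two changes of 0.3, 0.5 or 0.7; telomere length independent of SF-36; one SF-36 score; and tests at two-sided 5%. In the ANOVAs and follow-up tests, telomere change counts in either direction and SF-36 change only if it is an improvement, as the null is worded. Each case used 40,000 simulated studies at N = 10 and N = 20.

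**Three analyses compatible with the wording.**

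1. Joint test: Hotelling's T² on the p = 4 mean changes (two outcomes, two follow-ups), with F = (N − 4)T² / [4(N − 1)] on 4 and N − 4 degrees of freedom. It has no direction for either outcome.
2. Two ANOVAs: one repeated-measures ANOVA per outcome over three visits.
3. Four tests: a paired t-test for each outcome at each follow-up.

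**Any part suffices: probability of a go**

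| Analysis | Nothing changes, N = 10 or 20 | SF-36 shift 0.3 SD, no telomere effect, N = 10 | Same, N = 20 |
|---|---|---|---|
| Joint test | about 5% | 8–9% | 14–18% |
| Two ANOVAs | 7–8% | 16–20% | 26–32% |
| Four tests | 12–14% | 27–31% | 40–46% |

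The ranges cover the three correlations. Closed-form checks, treating the tests as independent: two tests, 1 − 0.95 × 0.975 = 7.4%; four tests, 1 − 0.95² × 0.975² = 14.2%. Correlation between follow-ups pulls the second figure down slightly.

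**If SF-36 scales are tested separately.** The plan does not say which score is used. The background on Chinese calligraphy lists eight scales for an earlier study. If those eight were tested here at both follow-ups, there would be 2 + 16 = 18 tests. With an assumed inter-scale correlation of 0.3 to 0.7, the false-go rate would be 23–35%. Both the use of eight scales and their correlation are assumptions.

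**Any part against every part.** Take a true lengthening of 0.8 SD of change and no SF-36 change, with four tests. If any part suffices, the rule fires in 76–83% (N = 10) or 97–99% (N = 20). If every part must be significant, it fires in at most 0.7%.

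**A single directional criterion.** Go if the lower limit of the two-sided 95% confidence interval for mean telomere change exceeds zero. The probability is that of a noncentral t with N − 1 degrees of freedom and noncentrality d√N exceeding 2.262 (N = 10) or 2.093 (N = 20).

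| True lengthening d (SD of change) | N = 10 | N = 20 |
|---|---|---|
| 0 | 2.5% | 2.5% |
| 0.3 | 13% | 25% |
| 0.5 | 29% | 56% |
| 0.8 | 62% | 92% |

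**The case against.** The strongest reply is that the plan speaks of one null and one p-value, and a single multivariate test of a joined null is a natural way to carry that out. Such a test holds the false-go rate at about 5%. A reader might infer that the rule must exceed 5%; the documents do not support that, because they fix neither the test nor the number of tests. What remains is that the joint test is not specified, and that it too can reject on an SF-36 shift alone.

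Second, the telomere focus in sections 1.0 and 2.0 may show that the sponsor meant telomere change to decide. That is plausible, but these passages state a purpose, and the trigger refers only to the joined null. The supportable claim is that an SF-36 gain can launch the trial, not that it will.

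Third, a reader might infer that failing to reject means no further trial. The plan gives only a sufficient condition, and section 4.0 mentions the future randomised study without any condition. That non-rejection stops the programme is an inference.

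Fourth, two other passages may look like evidence and are not:

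- The budget does not settle how many assays each person has or which result decides. The unit price is labelled per subject, so 20 units could be 20 subjects or two assays for each of 10, and the 2-cell option is not explained.
- The 2-month label on the last blood draw in section 9.0 reads as a slip, since the schedule elsewhere gives 9 months.

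Finally, this is a pilot. That limits the consequence but does not remove it, because the pilot itself sets a significance gate for a randomised trial.

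**Conclusion.** The concern holds: as written, the rule can fire on a signal other than the stated purpose. This follows from the wording alone. The probabilities rest on the assumed correlations, normality, number of tests and 0.3 SD shift. They range from no inflation with a joint test to more than double the nominal 5% with four follow-up tests, and higher if SF-36 scales are tested separately. For a true 0.8 SD lengthening alone, the choice between any part and every part moves the result from likely or near certain to almost never.

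Shortening is a literal consequence of the wording; no probability is attached to it, because the documents support no decline of a given size. Nor does the point show a false claim of efficacy: the consequence concerns the decision to launch a later trial. It should be fixed before results are seen.

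**What to change.** In section 1.0 (Hypothesis) and section 2.0 (Design of the Study), replace the joined null as the trigger with one primary hypothesis: the mean within-person change from baseline in one named telomere measure, at one named follow-up, in the direction of lengthening. One workable criterion is that the lower limit of the two-sided 95% confidence interval lies above zero; it is not the only acceptable choice. Report SF-36 and the other time point as secondary, outside the trigger. Say whether failing the criterion means that the follow-on trial is not run. Word the conclusion as within-person change, not efficacy.

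The cost is a few sentences, with no extra participants or assays. Two downsides should be written into the plan:

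- The chance of a go is only 13% (N = 10) or 25% (N = 20) for a true lengthening of 0.3 SD of change, so missing the criterion does not show absence of effect.
- Without controls the criterion cannot separate treatment from assay drift or other non-treatment change. A 0.3 SD rise from such causes would fire it equally often, and the 2.5% false-go rate holds only if there is none.

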- Adult subjects / patients (age 60 years and over) we expect at 60 years people have already measurable shortening of telomeres
- Healthy or III, with the exception of genetic illnesses and cancer (for which treatments could negatively impact telomeres)
- Willingness and ability to comply with data collection requirements.
- Complete submission of required documentation prior to enrollment into the study, including informed consent and consent to release of information.
- Willingness to allow their data to be used for research purposes and published as deemed fit (while conforming to all applicable privacy laws) by Sha Research Foundation.
- Willingness to practice the daily calligraphy meditations and follow the protocol.

Exclusion criteria

- Not meeting any of the inclusion criteria

- Bipolar disorders, other serious mental disorders (e.g. schizophrenia, psychosis), genetic illnesses (primarily affected chromosomes), and cancer (treatment could negatively impact telomere during research period)

- inability to sign consent and follow instructions

- Unwillingness to participate in data gathering

- Unable to follow the practice regimen, including the daily calligraphy meditations

- Pregnant or nursing. Participants who become pregnant during the study will be required to end their participation. (to avoid any, at current time unknown, potential negative effect of the study on the fetus).

- There are no exclusion criteria placed upon potential subjects related to national origin, culture, ethnicity, race, sex, physical disability, sexual orientation, religion, or spiritual practices.

4.0 Sample Size:

A/ Sample Size:

The study will be conducted as a simple follow up study. It will include subjects / patients who are at least 60 years old at the time of the examination.

The number of cases estimated was 10 (minimum) <= N <= 20 (maximum).

For the future formal randomized study, we will calculate the power (based on this pilot study).

The evaluation of the improvement in the Lengthening of Telomeres and Quality of Life questionnaires is done by means of the program Minitab or SPSS / PSPP using appropriate parametric and non-parametric tests: For statistical analysis of scores obtained from questionnaires we will use Anova and regression analysis, with confidence level set at 95%.

5.0 Recruitment and Screening Methods:

Recruitment announcement with be placed at:

Sha Research Foundation website: www.ShaResearchFoundation.com

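### An uncontrolled pilot cannot establish efficacy, and sizing the formal trial on its observed change would undersize that trial if a significant telomere result opens the gate

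*Combined protocol and SAP*

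**What the plan says.** The Objectives in section 1.0 open with: "The study is intended to measure the effects and determine the efficacy of Tao Calligraphy mindfulness practice". METHOD repeats the aim: "This study will determine the effects of transmission of a subtle energy and mindfulness practice with Tao Calligraphy". Design of the Study states that there is no control group because this is a pilot, and that every participant receives the intervention. Study Execution has participants continue their conventional treatment and encourages them to keep up their usual spiritual practices.

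The next step depends on the result. Under Design of the Study: "should the 0 Hypothesis be successfully rejected, this study will be followed by a formal Double Blind Randomized Crossover Study". Under Hypothesis in section 1.0: "if we receive p < 0.05, then H0 is rejected", and "Statistical test such as Anova will be used to evaluate the null hypothesis". The null has two parts. Participants "will have no significant change in telomere length in follow-up analyses", and they show no improvement on the RAND SF-36. The plan does not say which part must be rejected.

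Section 4.0 gives the size: "The number of cases estimated was 10 (minimum) <= N <= 20 (maximum"). It then says "For the future formal randomized study, we will calculate the power (based on this pilot study"). It does not say which pilot quantity enters that calculation. It gives no worthwhile difference, SD or target power.

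**The concern.** The objective claims something the design cannot deliver. A significant within-person change would be read as efficacy, although nothing in the study shows what would have happened without the intervention.

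The second issue is what the pilot passes on. It decides whether the formal trial starts, and it feeds that trial's power calculation. When an estimate is carried forward only if it is significant, small studies pass on mainly their overestimates. If the observed telomere change were used in this way, the formal trial could be planned far too small and miss a real effect. The uncontrolled change is also not the quantity a crossover estimates, which is a difference between treatment conditions.

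**Working it through.** **The plan's own figure.** The range of 10 to 20 cannot be reproduced, because no effect, SD or power is attached to it. For orientation, a two-sided paired t-test at 0.05 has 80% power at a standardized change d (mean change / SD of change) of 0.996 with 10 people and 0.660 with 20.

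**Efficacy claim.** Suppose the intervention does nothing but telomere length drifts by 0.5 SD for other reasons. The paired test then gives p<0.05 in 29% of pilots of 10 and 56% of pilots of 20. Rejecting the null therefore does not identify the cause. Regression to the mean is more plausible for SF-36 than for telomere length, because entry is not restricted by a telomere measurement.

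**Sizing: assumptions.** N of 10 or 20 and p<0.05 come from the documents. Not in the documents, and assumed here: a two-sided paired t-test, an 80% power target, the same d in both studies, and a range of true d.

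**Step 1: smallest significant change.** d_crit = t(0.975, N−1)/√N.
- N=10: 2.262/3.162 = 0.715
- N=20: 2.093/4.472 = 0.468

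**Step 2: ceiling on the plan.** The smallest n with 80% noncentral-t power is 18 at d=0.715 and 38 at d=0.468. No pilot that passes on this test can lead to a larger plan. With 8 or 16 completers the ceilings are 14 and 30.

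**Step 3: typical result.** 600,000 pilots were simulated per setting (mean ~ N(d, 1/N), SD from chi-square). Significant increases were kept, n was planned at the observed d, and power was evaluated at the true d. Entries are for pilots of 10 / 20.

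| True d | Pilots passing | n needed | Median planned n | Actual power | Plans large enough |
|---|---|---|---|---|---|
| 0.3 | 13% / 25% | 90 | 13 / 25 | 17% / 30% | 0% / 0% |
| 0.5 | 29% / 56% | 34 | 12 / 21 | 35% / 59% | 0% / 10% |
| 0.8 | 62% / 92% | 15 | 10 / 14 | 62% / 79% | 16% / 46% |
| 1.0 | 80% / 99% | 10 | 9 / 10 | 75% / 80% | 42% / 57% |

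**Step 4: is the gate the cause?** Without it, the median plan is 85 / 87 at d=0.3 and 32 / 33 at d=0.5, with power of 78–80%. The gate therefore drives the shortfall in the median plan.

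**Step 5: ANOVA instead of a t-test.** The gate is now a three-visit repeated-measures F test with independent equal errors, and the formal trial is sized on the 9-month change. Power at the median plan is 17–18% / 29–31% at d=0.3 and 32–38% / 54–61% at d=0.5. The result is similar, but 18 / 38 is no longer a hard ceiling.

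**Step 6: SF-36 can also open the gate.** Let an independent SF-36 result pass with probability q (not in the documents). Power at the median plan:

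| q | d=0.3 | d=0.5 |
|---|---|---|
| 0 | 17% / 30% | 35% / 59% |
| 0.3 | 48% / 43% | 47% / 65% |
| 0.5 | 64% / 61% | 59% / 69% |
| 0.8 | 74% / 74% | 74% / 75% |
| 1 | 78–80% | 78–80% |

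**Step 7: only the SD is carried over.** At d=0.3 the median plan after a telomere gate is 58 / 76, with power of 61% / 73%. The shortfall is milder.

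**Step 8: a different quantity.** Under the error assumption of step 5, a crossover comparing changes from each period's baseline has an SD √2 = 1.41 times as large. The need then rises from 90 to 177 at d=0.3 and from 34 to 65 at d=0.5.

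**The case against.** The strongest reply is that the sizing harm depends on two things the documents do not say. Section 4.0 never commits to the observed change; the sponsor could take only the SD. And because the null is compound, an SF-36 result could open the gate. That route is realistic, since the Background and Potential Benefits sections report SF-36 improvement in earlier studies of the practice. From q=0.5 upward, power at the median plan is above one half at both d=0.3 and d=0.5. This stands, and it makes the sizing half conditional. Some shortfall remains at q=0.3 and 0.5, so the point weakens but does not vanish.

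It is also fair that the inputs to a future trial belong in that trial's protocol, and that the plan openly explains the missing control group and defers randomization. That defends the design. It does not defend an efficacy objective attached to it.

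Two stronger readings are tempting. A reader might infer that the formal trial will be underpowered; the documents do not support this, because the quantity and the gating endpoint are both unstated. A reader might also infer, from the statement that telomeres shorten with age, that the direction of bias is unknown. That does not follow: shortening alone would work against finding lengthening. The firm point is only that the change cannot be attributed to the intervention.

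**Conclusion.** The objective wording is wrong as written. A single-group before-after study cannot determine efficacy or effects, and rejecting the null at p<0.05 does not change that. This part needs no numerical assumption.

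The sizing part is conditional and of lower weight. If telomere length opens the gate and the observed change is used, a nominal 80% trial has about 17% / 30% power at d=0.3 and 35% / 59% at d=0.5 after pilots of 10 / 20. There is little harm at d of 0.8 or more with 20 people. The shortfall shrinks as SF-36 opens the gate more often, and in the median plan it largely disappears if SF-36 always does. These figures rest on the assumed d, test and power target. They apply only to pilots that pass: at d=0.3 with a telomere gate, 87% / 75% do not, and the fix does not alter that. In every case the uncontrolled change is not the treatment difference on which a crossover is sized.

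**What to change.** **Section 1.0, Objectives**, replace the first sentence with: *The study is intended to estimate the within-participant change in telomere length in peripheral blood leucocytes during Tao Calligraphy mindfulness practice together with subtle energy transmission. Without a control group this change will not be attributed to the intervention.*

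**METHOD**, opening sentence: replace the claim to determine effects with *describe the changes following*. Make the same change where the rationale, just before METHOD, says the project focuses on effects.

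**Section 4.0**, replace the sentence on power with: *The formal study will be powered for a minimum worthwhile difference fixed before the pilot data are analysed, not for the change observed in this pilot. The pilot supplies only the SD of within-person change in telomere length, with allowance for its imprecision at the actual number of completers. The SD of the crossover treatment difference will be justified separately.* One possible allowance is the upper one-sided 95% limit, which multiplies the SD by √((n−1)/χ²(0.05, n−1)) for n completers: 1.645 for 10 and 1.370 for 20. Choosing that limit is a trade-off between assurance and size.

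**Design of the Study**: state which endpoint must be significant for the formal study to proceed.

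**Cost.** Wording, the work of justifying a worthwhile difference, and a larger planned formal trial. With the upper 95% limit, the median n for d=0.3 is about 154 / 141 after a telomere gate, or 221 / 161 without one, against 90 if the SD were known. For d=0.5 it is 63 / 55 or 81 / 59, against 34. The conduct of the pilot does not change.
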